Summary of Experiment & Research Design: Twenty-eight subjects will participate in a novel training paradigm targeting lower extremity muscle function. Training will take place over an 8-week period, three times per week on non-consecutive days. Exercises will be performed in the paretic and non-paretic limbs separately and progressed as tolerated across the 8-week period. Dynamometric evaluations of isokinetic strength and isotonic power will be performed prior to, after 4 and 8 weeks of training as well as 8 weeks following cessation of training (Figure 13). Assessments of muscle morphology (CSA) and in-vivo bioenergetics (PCr recovery and [Pi]) as well as full biomechanical assessments of walking will be performed at the same time points, allowing determination of the efficacy (and persistence) of training on the proposed outcomes. We will perform walking analysis over-ground and on the instrumented treadmill by collecting: (i) kinetics (3-dimensional ground reaction forces and moments), (ii) kinematics and iii) EMG from each leg. For each kinesiological measure, averages over the gait cycle for each leg will be calculated for each subject. Our primary outcome measures during biomechanical assessments will be peak ankle plantar flexion and knee extension power generation, with secondary variables of interest to include paretic step length ratio and paretic propulsion. A battery of clinical assessments to evaluate degree of function and disability will be performed prior to as well following training and at the 8 week post-training time point (see **Procedures-Specific**).

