Data Analysis Plan: To quantify the effects of our POWER training intervention on neural and muscular adaptations, we will utilize repeated measures mixed effects regression models to assess for significant changes in our outcomes over time. Neural and muscular adaptations (on both the paretic and non-paretic legs) will serve as dependent variables in separate models, with time serving as the key independent variable in each. Various error structures associated with the repeated measures over time will be considered (e.g. compound symmetry vs. auto-regressive), and final error structures will be selected based on AIC values. Having random subject effects in the models will account for correlation among measures within subjects over time. Secondary analyses, incorporating differences in the paretic and non-paretic legs as dependent variables, will examine whether changes over time are more pronounced in the paretic vs. non-paretic leg. These models will also incorporate random subject effects to account for within-subject dependence. Error correction will be set to maintain type one error at 5% with a desired power of 80%.

Expectation: We hypothesize that POWER training will result in significant increases in muscle peak power generation, central activation, muscle CSA and in-vivo oxidative capacity as well as a concomitant decrease in [Pi]. Further, we expect changes in these variables will be greater in the paretic compared to the non-paretic leg. We also expect improvements in Clinical Assessments as a result of training as well as increases in our measures of locomotor function (see **Procedures-Specific**).

Innovation: Through conduct of the proposed experiments, we will generate a rich data set, capable of relating measures of lower extremity power generation (both in and away from the task of walking) with functional walking performance. The proposed neuromuscular assessment

[figure not shown]

Figure 13: Timeline for measures during POWER training

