Sample size determination and Statistical Approach: A total of 28 subjects will be recruited for this study. With baseline data from n=28 subjects, we will have at least 80% power to detect measures of association (i.e. partial correlations) as small as 0.5 between neural/muscular adaptations and peak power generation. Our preliminary data suggest that the intraclass correlation between measures of power on paretic and non-paretic legs is extremely high (i.e. Spearman rho = 0.81, intraclass correlation coefficient [ICC - from mixed model] ~100%). This power estimate for Aim 1 is based on 1 observation per subject; although our mixed model approach for analyses for Aim 1 will include 2 observations per subject (i.e. paretic and non-paretic leg), the detectable correlation may not be substantially lower due to the strong intraclass correlation. For Aims 2 and 3, analyses rely on longitudinal measures, and we assume (based on experience with our patient population) that no more than 15% will fail to complete all assessments. With 28 subjects enrolled and a 15% attrition rate over time (resulting in complete data on 24 subjects), we would have at least 80% power to detect changes in measures from baseline to the end of the study equivalent to 0.6 standard deviation units (i.e. effect sizes). This power estimate is based on a paired t-test framework (i.e. pre-post comparisons), and thus power is likely underestimated, since our models will also include data from mid-intervention and follow-up time periods. For example, assuming an ICC of 90% associated with within-subject responses over 4 time periods, the effective sample size (see Campbell et al., 2001) would be slightly higher (~n=26), as would be our power (~83%) to detect an effect size of 0.6. Treatment effect sizes of 0.6 are consistent with our preliminary data, in which effect sizes of 0.7 (95% CI 0.5 to 0.9), 1.5 (95% CI 1.1 to 1.9, and 0.5 (95% CI 0.1 to 1.0) were observed for improvement in gait speed, paretic leg power, and non-paretic power, respectively. With complete data on 24 subjects, we will also be able to detect whether as little as 40% of the variability in changes in gait speed can be explained by changes in the neural / muscular adaptation measures, assuming an ICC of 90% associated with within-subject responses over 4 time periods. All power estimates assume 2-sided hypothesis tests and an alpha level of 0.05 and were conducted by a biostatistician using PASS 2008 (NCSS, Kaysville, Utah).

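### Aim 2 promises error correction at 5% with 80% power, but the stated 80% is the power of one uncorrected test

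*Combined protocol and SAP*

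**What the plan says.** The Aim 2 data analysis plan says: "Neural and muscular adaptations (on both the paretic and non-paretic legs) will serve as dependent variables in separate models". Time is the key independent variable, and secondary models compare the legs. The paragraph ends: "Error correction will be set to maintain type one error at 5% with a desired power of 80"%. It gives no correction method, no list of the tests covered and no ranking of outcomes.

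The Aim 2 expectation puts five outcomes on an equal footing: peak power, central activation, cross-sectional area (CSA), oxidative capacity and inorganic phosphate. Primary measures appear in two lists. The Aim 2 design summary says: "Our primary outcome measures during biomechanical assessments will be peak ankle plantar flexion and knee extension power generation". The Aim 1 design summary gives four numbered groups of primary measures in two muscle groups.

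The sample-size section claims, for 24 completers out of 28 enrolled, "at least 80% power to detect changes in measures from baseline to the end of the study equivalent to 0.6 standard deviation units". It adds "This power estimate is based on a paired t-test framework (i.e. pre-post comparisons", and then "All power estimates assume 2-sided hypothesis tests and an alpha level of 0.05". It does not mention multiplicity.

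**The concern.** The two sections do not meet. One promises a correction over several models together with 80% power; the other computes 80% as if only one test were done and nothing corrected. A correction that covers several outcomes lowers the power of at least some of the tests, and the plan does not say by how much.

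Two misreadings could follow:

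- **If a correction is applied,** a non-significant change in, say, CSA could be taken as no training effect, on the belief that the test had 80% power at 0.6 SD.
- **If none is applied,** the chance of at least one false training effect exceeds the 5% that the sentence appears to promise.

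Either way, a reader cannot tell which Aim 2 result is protected at 5% or which one the 80% describes. The family and method could also be chosen after the results are known.

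**Working it through.** **Inputs from the sample-size section.** 28 enrolled, 15% attrition, 24 completers, effect 0.6 SD, two-sided alpha 0.05, paired t-test, within-subject correlation 0.90 over 4 time points.

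**Step 1: reproduce the plan's figures.** Power of a two-sided paired t-test comes from the noncentral t distribution with n − 1 degrees of freedom and noncentrality 0.6 × √n.

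- Completers: 28 × 0.85 = 23.8, or 24.
- n = 24, alpha 0.05: 80.4%. The plan says at least 80%.
- Effective n: 24 × 4 / (1 + 3 × 0.9) = 96 / 3.7 = 25.9. The plan says about 26.
- n = 26, alpha 0.05: 83.6%. The plan says about 83%.

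The figures are right for one uncorrected test.

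**Step 2: assumptions for an illustration.** The plan gives no number of tests. I take the five outcomes in the Aim 2 expectation, ignoring the further multiplication by leg and muscle group. Every effect is set at 0.6 SD. The documents give no correlations between change scores, so these run from 0 to 0.9.

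**Step 3: apply a correction.** Bonferroni uses 0.05 / 5 = 0.01 in the Step 1 formula. Holm and Hochberg were simulated with equally correlated normal change scores (100,000 trials per setting). Repeat simulations agree to about one percentage point.

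| Five tests, 0.6 SD each | n = 24 | n = 26 |
|---|---|---|
| Bonferroni, per test | 56% | 61% |
| Holm, average per test | 65–69% | 69–74% |
| Hochberg, average per test | 71–72% | 75–77% |
| Holm, at least one detected | 71–98% | 75–99% |
| Bonferroni detectable effect, 80% power | 0.75 SD | 0.72 SD |

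For one test at n = 24 the detectable effect is 0.60 SD. With only two tests under Holm at n = 26, average power is 79–81%.

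**Step 4: compare with the plan's preliminary effects.** This takes those effects to be on the same scale as the 0.6 SD.

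- Paretic power, 1.5: well above 0.75, so safe under correction.
- Gait speed, 0.7: above 0.60 but below 0.75.
- Non-paretic power, 0.5: below 0.60 even without correction.

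The sample-size section gives no effect size for central activation, CSA, oxidative capacity or phosphate.

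**Step 5: no correction.** With five true nulls, familywise error is 1 − 0.95⁵ = 22.6% if the tests are independent, and about 10% at correlation 0.9.

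**The case against.** The strongest reply is that this is a single-arm mechanistic study of 28 people, and that the sample-size section openly states its single-test basis and computes it correctly. That stands: nothing in the section is miscalculated. But the correction is the plan's own promise, and the section does not reflect it.

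A second reply is that the sentence is ambiguous. It closes a paragraph on error structures and random effects and never mentions multiple comparisons, so it may mean only a nominal 5% per test. That is possible. In that case there is no multiplicity control and Step 5 applies, so the sentence still needs clarifying.

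Three stronger readings are tempting, and the documents do not support them:

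- **That 5% and 80% cannot be held together.** This depends on the family, the method and what power means, none of which is given. Two tests under Holm at n = 26 stay near 80%. The first test in a fixed sequence keeps its 80%. The chance of detecting at least one of five effects exceeds 80% unless the correlation is very high.
- **That the powered visit is undefined.** The end-of-study wording is loose. However, the section calls the comparison pre-post and counts mid-intervention and follow-up data as additional, which points to the end of training.
- **That no primary outcome is named.** Several are. The Clinical Assessments section even speaks of a targeted primary outcome in the singular, in the context of walking, but without naming a measure. What is missing is a single test to which the 5% and the 80% attach.

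**Conclusion.** The point holds in this form: Aim 2 promises error correction with 80% power, and the sample-size section's 80% does not include any correction. The size of the gap cannot be fixed from the documents, because family and method are unstated.

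The illustrative loss is from 80% to between 56% and 72% per test at n = 24, or from about 84% to between 61% and 77% at n = 26. It rests on three assumptions: a family of five, equal 0.6 SD effects, and correlations from 0 to 0.9. It describes per-test power only and would fall unevenly, sparing paretic power if the preliminary effect is near the truth. The plan should be corrected, but this is a mismatch between two sections and not evidence that the study is too small for every aim.

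**What to change.** Before results are seen:

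1. In the sample-size section, state that the 80% is the power of a single test at unadjusted two-sided 0.05.
2. In the Aim 2 data analysis plan, take one of two routes.
   - Name one primary outcome, with leg and muscle group (the sponsor's choice), for the change from baseline to the end of training at 0.05. Label the rest either secondary under a named familywise method, such as Holm or a fixed sequence, or exploratory.
   - Or define the family and the method, and restate power or detectable effect at the corrected alpha (for example 0.75 SD for five tests, Bonferroni, n = 24).
3. As a tidy only, replace the end-of-study reference in the power statement with the visit meant.

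The cost is wording in two sections, with no extra participants or data. The downside is that the stated power for the non-primary outcomes becomes less favourable, and the sponsor must commit to a primary outcome or a family.

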Summary: The consequences of alterations in skeletal muscle post-stroke are far reaching and contribute to decreased motor control and overall fitness, development of functional limitations, and long term disability. We have highlighted several adaptive changes that occur that contribute to muscle dysfunction in persons post-stroke when compared to neurologically healthy individuals. To date, however, the relative importance of these factors as well as whether and how these impairments relate to existing functional deficits is yet unknown. Furthermore, the extent to which these alterations are amenable to rehabilitation training and the degree to which changes in these properties relate to functional improvements would be valuable information to help guide therapeutic decision making in the treatment of post-stroke locomotor dysfunction.

Plantar flexor muscle power generation is associated with locomotor function post-stroke: Individuals following stroke typically present with some degree of residual motor function. The extent of this residual function varies greatly from person to person, and significant locomotor impairments often persist. Although a number of factors likely contribute to slow walking, we examined the importance of muscle power generating capacity of the plantar flexor muscle group during dynamometric strength testing in predicting locomotor ability in individuals with chronic post-stroke hemiparesis (n=23). Ankle plantar flexor power was determined bilaterally. In addition, self-selected gait speed was measured during over-ground walking. Significant correlations were

found between self-selected gait speed and ankle power in the paretic ($r = 0.78$) and non-paretic ($r = 0.46$) legs (Figure 5). The strength of the correlation between the paretic PF muscle group and gait speed suggests the importance of ankle power in predicting locomotor ability post-stroke and suggests paretic PF function as a potential target for improving locomotor ability in this large clinical cohort.

[figure not shown]

Figure 5: Correlations between self-selected gait speed and plantar flexor power in the paretic (left) and non-paretic (right) legs.

Paretic ankle powers relate to locomotor performance:

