Effects of POWER training on persons post-stroke: We recently completed data collections on five individuals (4 males; 62.4 ± 7.3 yrs; 45.2 ± 25.7 mos. post-stroke) who completed 24 sessions of POWER training. Training resulted in increases in self-selected and fastest comfortable walking speeds, improved walking endurance, as well as bilateral increases in muscle strength and power generation. Specifically, overground self-selected walking speed (SSWS) increased from 0.58 ± 0.24 m/s to 0.78 ± 0.28 m/s following training. Similarly, fastest comfortable walking speed increased on average from 0.91 ± 0.32 m/s to 1.35

[figure not shown]

Figure 10: Bi-weekly gait speeds for individual subjects completing POWER training.

± 0.52 m/s. Bi-weekly measures of SSWs suggest continuous improvements over the 8 week period (Figure 10). Of note, the average increase in gait speed (i.e., 0.20 m/s) for our group ($n=5$) exceeds the clinically meaningful difference recently reported for participants in the recently completed LEAPS trial. Increases in gait speed for individual subjects were also accompanied by increases in paretic hip, knee and ankle joint powers. Of note, peak paretic ankle power increased by an average of $\sim 31\%$ during walking at self-selected speed between the pre- and post-training time points. This increase is important as it provides evidence of carry-over from training-induced improvements in muscle power generation to task-specific performance (Individual subject power profiles shown in Figure 11). Non-paretic ankle power during decreased $\sim 12\%$, suggesting that compensatory strategies at the ankle were not associated with behavioral improvements. In addition to changes in gait speed, subjects realized average improvements in 6 minute walk test (6MWT) of $(139.8 \pm 47.6$ ft.), a change shown to be clinically important.

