Rationale: Given that in persons post-stroke, improving walking is 1) independently related to overall health status; 2) a strong predictor of functional recovery and 3) the most often stated goal during rehabilitation, interventions aimed at improving functional walking status are critical to increasing independence and improving quality of life for patients and their caregivers. The advanced methodologies proposed herein and the novel theoretical framework we have developed allow for detailed investigation of the neural and muscular factors that contribute to (changes in) muscle power generation. In addition, the state-of-the-art assessments of walking provide a comprehensive evaluation of locomotor behavior and the biomechanical mechanisms underlying hemiparetic walking performance. Moreover, we seek to identify the muscular characteristic(s) that best predict functional improvement and provide evidence establishing the characteristics of those most likely to benefit (or not) from training.

Summary of Experiment & Research Design: We will determine the relationship between changes in neural and muscular factors and improved power generation following training. We will also assess functional improvements via the proposed clinical assessments as well as through full biomechanical evaluations of walking.

Data Analysis Plan: We will assess relationships for changes in central activation, muscle CSA and [Pi] (predictor variables) with improvements in muscle power generation (criterion variable) and self-selected walking speed by using mixed effects regression models, which, by incorporating random subject effects, will allow us to account for correlation of measures made on the same individual over time. We will also use measures of muscle power generation in the paretic and non-paretic knee extensor and plantar flexor muscle groups as predictor variables in a multivariable linear regression model to assess relationships with self-selected walking speed. Standardized β coefficients from these regression models will help us determine which factors have the strongest influence on our outcome variables (i.e. power generation and self-selected gait speed).

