- **Stroke Impact Scale (SIS):** The SIS assesses physical function as well as other dimensions of health-related quality of life: emotion, communication, memory & thinking, and social role function. The SIS was created to assess changes in impairments, disabilities and handicaps following stroke, but has been validated for repeated administration over time, in clinical and research settings (Duncan et al., 2003 a,b,c).

Projected Timetable:

- **Project Development:** The first quarter (Months 1-3) of Year 1 will be devoted to finalizing imaging sequences for MRI and ^{31}P -MRS studies and establishing the data acquisition pipeline for dynamometric and biomechanical data collections.
- **Subject Recruitment:** Recruitment of participants will begin early in the first quarter of the project period and will continue through the third quarter of year three.
- **Longitudinal Evaluations:** Baseline evaluations prior to POWER training will take place beginning in Quarter 2 of Year 1 and continuing through the end of Year 3. We will evaluate muscular function and perform MR imaging and spectroscopy studies to determine muscle power, central activation, muscle cross-sectional area, [Pi] and *in-vivo* oxidative capacity of the plantar flexor and knee extensor muscle groups.
- **Therapeutic Intervention:** Beginning in Quarter 2 of Year 1 and continuing through Quarter 2 of Year 4, hemiparetic subjects will participate in 8-weeks of POWER training.

- **Follow-up Evaluations:** Post-training evaluations will be conducted 8 weeks following POWER training. Assessments performed at pre- and post-training will be repeated during follow-up evaluation.
- **Data Analyses:** Data analysis will begin beginning in Year 3 and throughout the remainder of the project.
- **Dissemination:** Data dissemination will take place as appropriate, but not earlier than in Year 3, via meeting abstracts as well as full publications.

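### The Aim 3 change-on-change models name no baseline covariate, so shared dependence on starting level could be read as an effect of adaptation; the size is unknown and probably modest

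*Combined protocol and SAP*

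**What the plan says.** In the combined protocol and SAP, section D, Aim 3, Data Analysis Plan, the first set of models relates "changes in central activation, muscle CSA and [Pi] (predictor variables) with improvements in muscle power generation (criterion variable") and with self-selected walking speed. The models are mixed-effects regressions which, "by incorporating random subject effects, will allow us to account for correlation of measures made on the same individual over time". A second model uses knee extensor and plantar flexor power "as predictor variables in a multivariable linear regression model to assess relationships with self-selected walking speed". Standardized coefficients from these "regression models will help us determine which factors have the strongest influence on our outcome variables".

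No baseline value of a predictor, of power or of walking speed is named as a covariate. Elsewhere, baseline power enters a model only in Aim 1, as the dependent variable. The section on screening and clinical assessments foresees a retrospective look at range of motion, spasticity and sensation against response, which is not adjustment for starting level.

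The baseline data will exist. The Projected Timetable says "Baseline evaluations prior to POWER training will take place beginning in Quarter 2 of Year 1" and lists power, central activation, CSA and [Pi]. Under Aim 2, strength and power tests "will be performed prior to, after 4 and 8 weeks of training as well as 8 weeks following cessation of training", with CSA, [Pi] and walking assessed at the same times.

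**The concern.** Aim 3 is meant to show which adaptations go with functional gain, and its coefficients will be used to rank them. The study has one trained group, so no comparison arm separates a mechanism from patients simply changing according to how impaired they were at entry. If more impaired patients have more (or less) room to change on both measures, the two changes move together even when one does nothing for the other. If the dependence runs in opposite directions, a real association is partly hidden. In either case the ranking would partly describe initial severity.

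**Working it through.** **The plan's own figures.** 28 × 0.85 = 23.8, so 24 completers, as stated under Sample size determination and Statistical Approach. That section claims that 40% of the variability in gait-speed change can be detected. With n = 24, the three listed change predictors and two-sided alpha 0.05, the noncentrality is 24 × 0.40/0.60 = 16 and power is 87.4%. The claim holds, and this point does not affect the sample size.

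**Size of the artefact.** Let ρ be the correlation between the two baselines, and a and b the correlation of each change with its own baseline. With no direct link between the changes, the correlation between them is ρ × a × b.

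Inputs:
- a and b: not in the documents; assumed.
- ρ for activation, CSA or [Pi] with power or speed: not in the documents; assumed from 0.3 to 0.78. The upper value is borrowed from section C, where a correlation was "found between self-selected gait speed and ankle power in the paretic" leg of r = 0.78 (23 people). Power and speed are both outcomes in the first Aim 3 models, so this is a stand-in only.
- n = 24, one pre-post change per person, baselines free of measurement error.

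Simulated rejection rate (40,000 trials per setting, no true link, nominal 5%):

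| a = b | ρ | ρab | Unadjusted | Outcome baseline added |
|---|---|---|---|---|
| 0.3 | 0.3 | 0.027 | 5.1% | 4.9% |
| 0.3 | 0.5 | 0.045 | 5.5% | 5.0% |
| 0.3 | 0.78 | 0.070 | 6.1% | 4.9% |
| 0.5 | 0.3 | 0.075 | 6.4% | 4.9% |
| 0.5 | 0.5 | 0.125 | 9.0% | 4.9% |
| 0.5 | 0.78 | 0.195 | 14.8% | 5.1% |

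A separate run of 5,000 trials gave 6.8% for a = b = 0.3 at ρ = 0.78, and 6.9%, 8.7% and 15.4% for the three rows with a = b = 0.5. With a and b of opposite sign the product is negative (0.78 × −0.5 × 0.5 = −0.195) and works against a true positive association.

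**Self-selected speed.** This is the only outcome of these models with pilot standard deviations: 0.24 m/s before and 0.28 m/s after training (section C, five people). For an assumed pre-post correlation r, the change-baseline correlation is (r·s1 − s0)/√(s0² + s1² − 2·r·s0·s1). At r = 0.9 this is (0.252 − 0.240)/√0.01504 = 0.012/0.1226 = 0.10. With a = 0.5 and ρ = 0.78 the artefact is 0.78 × 0.5 × 0.098 = 0.04, and the simulated rate is 5.4%. Across other values of r:
- r = 0.8: b = −0.10, rate 5.2%
- r = 0.6: b = −0.31, rate 8.7%
- r = 0.95: b = 0.29, rate 8.0%

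**Cost of adjustment.** Power at partial R² = 0.40 with three tested predictors and n = 24 is 87.4% with no baseline term, 87.0% with one, 86.6% with two and 85.6% with four.

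**Measurement error in the baseline.** With assumed reliability of 0.8 to 0.9, ρ = 0.78 and a = b = ±0.5, the rate is about 9 to 12% unadjusted and 5 to 7% with the outcome baseline added. If the outcome's gain does not depend on its true baseline (b = 0), the unadjusted test keeps 5%, while the adjusted test rises to about 6.5% at reliability 0.8 and a = ±0.7; other error settings reach about 7.6%.

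**The case against.** The strongest reply is that the bias is conditional and nothing in the documents sizes it. Both changes must depend on starting level and the baselines must be correlated; if either a or b is zero, the unadjusted test is sound. That stands, and it keeps the claim to what could happen.

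A reader might take the pilot's widening spread as proof that gain depends on baseline, for instance that "fastest comfortable walking speed increased on average from 0.91 ± 0.32 m/s to 1.35" ± 0.52 m/s, or the similar pattern in plantar flexor contraction velocity. The documents do not support this. Neither variable is in the models at issue. A wider spread also arises when response varies independently of baseline: for fastest speed the implied dependence is zero at a pre-post correlation of 0.32/0.52 = 0.62. With five people the data cannot tell these apart.

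A reader might also apply r = 0.78 to every predictor. It describes power with speed only; at ρ of 0.3 to 0.5 the rate with a = b = 0.5 is 6 to 9%.

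It would be too strong to say that adjustment always restores 5%, since that needs error-free baselines. Nor do the documents reject adjustment: they are silent.

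Finally, the model form is not settled. The wording could also describe level-on-level mixed models, and the power-to-speed regression is not clearly a change model. The point therefore applies to the change models. The random subject effect does not replace the covariate, because it addresses correlation among repeated measures, not the dependence of both changes on starting level.

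**Conclusion.** The point holds in a limited form. Read as change-on-change models, the first Aim 3 analyses omit baseline values that the trial collects, and an association could partly reflect initial severity. The false-positive rate is about 6%, 9% and 15% at ρ = 0.3, 0.5 and 0.78 if a = b = 0.5, and at most about 6 to 7% if a = b = 0.3. These rest on assumed correlations, 24 completers and error-free baselines. For self-selected speed the pilot suggests negligible bias at a pre-post correlation of 0.8 to 0.9, with five people behind that figure. The documents do not support saying that Aim 3 results will be spurious, or that the stated power is wrong. The change is worth making because it is nearly free and the coefficients will be used to rank mechanisms.

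**What to change.** In each Aim 3 model of change, add the baseline value of the outcome (peak power or self-selected walking speed) as a covariate. As a sensitivity analysis, also add the baseline of the predictor. Report the unadjusted estimate beside both. State which Aim 3 models are change models, so that it is clear where this applies.

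The cost is analysis-plan wording, with no new data, visits or participants. One or two added terms take one or two degrees of freedom and 87.4 − 86.6 = 0.8 points of power at partial R² = 0.40. If all three predictors enter one model, the sensitivity analysis carries four baseline terms and costs 87.4 − 85.6 = 1.8 points. Measurement error in the baseline can add a small bias of its own (up to about 7 to 8% false positives in an adverse case), which is why the adjusted and unadjusted estimates should both be shown.
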